#### STUDY SUMMARY

Title	A pilot study of the combination of 5-azacitidine (5-AZA) and all-trans retinoic acid (ATRA) for prostate cancer with PSA-only recurrence
Short Title	Prostate Cancer Dormancy
Protocol Number	
Phase	Pilot, phase 2
Methodology	Randomized, open label
Study Center(s)	Single-center
Objectives	
Primary
 

1) Evaluate disease progression-free rate at the end of Treatment Phase 1 between 5-AZA+ATRA and no-therapy.

2) Assess safety of the 5-AZA and ATRA combination therapy

 
Secondary:
 

1) Evaluate time to disease progression from start of Treatment Phase 1

2) Correlate antitumor activity and disease progression with biomarkers of dormancy in BM aspirates and peripheral blood

Number of Subjects	20 evaluable patients; the target accrual number is set at 30 to account for screen failures.

Diagnosis and Eligibility Criteria	
Diagnosis: Histologically confirmed adenocarcinoma of the prostate
 
Main inclusion criteria: 1) Rising PSA 2) PSADT <math>\leq</math> 10 months prior to initiation of ADT 2) 3) Received definitive local treatment 4) Indication for ADT 5) No evidence of regional or active distant metastases, except for regional metastases where salvage radiation therapy is not an option
 
Main exclusion criteria: 1) Patients who have received ADT and/or other chemotherapy within 3 months prior to entering the study. 2) Patients who have had radiotherapy or surgery within 4 weeks prior to entering the study. Minimally-invasive procedures for the purpose of diagnosis or staging of the disease are permitted.

Study Product(s), Dose, Route, Regimen	5-azacitidine: 40 mg/m  SQ on days 1-5 All-trans retinoic acid: 45 mg/m  PO daily (divided into 2 doses) on days 3-7 One cycle of treatment: 28 days
Duration of administration	Drugs will be administered on a 28-day cycle
Reference therapy	No reference therapy
Statistical Methodology	We will compare the disease progression-free rate at end of treatment phase 1 and time to disease progression from start of Treatment Phase 1 between 5-AZA+ATRA and no-therapy. Descriptive summary will be provided for safety endpoints and dormancy marker panel. The effect of biomarker abundance on recurrence free survival will be determined using Kaplan-Meier curves stratified across biomarker abundance groups.
Estimated enrollment period	12

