## 3. STUDY DESIGN

### **3.1 General Design**

This is a prospective, open-label, randomized, pilot study of reprogramming therapy in patients with recurrent PCa based on rising PSA only. Reprogramming therapy will include 5-azacitidine and all-trans retinoic acid. Expected duration of subject participation is 24 months.

All study will be assigned in a 1:1 randomization using computer random number generator to either the '5-AZA+ATRA' group or the 'no therapy' group. All enrollees will receive Leuprolide 7.5 mg x 1 on Day 1. On Day 29, they will initiate treatment phase 1. During this phase, patients in the '5-AZA + ATRA' group will receive treatment on a 28-day cycle, in the absence of prohibitive toxicities, for 3 cycles. During treatment phase 2, the 'no therapy' group will receive 5-AZA + ATRA on a 28-day cycle, in the absence of prohibitive toxicities, for 3 cycles. The treatment effect will be determined via comparing the intra-individual disease progression outcome at the end of the treatment phase 1, with period effect being separated through randomization. After treatment phase 1 and phase 2, all patients will be followed for a total of 24 months from the start of the study or until the events leading to discontinuation as outlined in Section 7.1 are observed. 5-AZA will be given subcutaneously on days 1-5 at a dose of 40 mg/m^2. ATRA, dosed at 45 mg/m^2 daily (divided into 2 doses), will be taken orally on days 3-7 of each cycle.

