### *Treatment Phase(s):*

Patients will be evaluated on day 1 of each cycle for assessment of adverse events and laboratory values. Peripheral blood will also be collected at day 1 of study prior to Leuprolide administration and day 1 of each cycle to perform dormancy signature assays. Patients will have an option to undergo BM biopsy to obtain aspirate at the end of the study period for dormancy signature assays. A restaging bone scan and CT A/P will be performed after every 3 cycles.

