## **8. STATISTICAL CONSIDERATIONS**

### **8.1 Study Design/Study Endpoints**

The primary endpoints will be the disease progression-free rate at the end of the treatment phase 1 and safety of the combination of 5-AZA and ATRA. Disease progression is defined by composite of PSA or radiographic progression relative to period baseline (start of treatment phase 1), whichever occurs first. PSA levels will be measured on day 1 of each cycle. For assessment of PSA progression, see section 3.2.1 above. CT A/P and bone scan will be performed every 3 cycles. For assessment of radiographic progression, see section 3.2.2 above. Safety will be assessed by the recording of adverse events, monitoring of vital signs and physical examinations, safety laboratory evaluations, and 12-lead ECG. Adverse events will be graded per the Common Terminology Criteria for Adverse Events (CTCAE) version 4.0. Therapy will be continued at the original dose if the adverse event is grade 0-2. For grade 3-4 toxicities, therapy will be held until improvement of symptoms to grade 2 or below. The dose will then be reduced by 25% of original for each episode. A maximum of 2 dosage reductions will be allowed. The third occurrence will result in removal of the patient from the study.

The secondary endpoints will be time to tumor progression from start of treatment phase 1 and the measurement of dormancy biomarker levels in relation to disease states: tumor progression and disease progression. To determine the relation between dormancy biomarkers and disease states, every 3 cycles, we will measure the dormancy biomarkers, TGF $\beta$ 2, BMP7, BMP4, GAS6, retinoic acid, NR2F1, in BM aspirates and peripheral blood.

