The micro-environmental biomarkers and dormancy biomarkers collected in this study will be described with summary statistics (mean, median, standard deviation, range) at each time point, and compared between the 5-AZA+ATRA and placebo using the Wilcoxon rank sum test statistics. Distribution of biomarkers will be examined and linear mixed model with random effects will be applied to analyze the biomarker trajectories over time. The biomarkers will be correlated with disease progression outcomes. Biomarker analysis will be performed on all patients with at least one biomarker measure at one time point (biomarker set).

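### The marker comparison in Section 8.4 names a placebo the trial does not have, sets no period although controls later take the drug, and gives the pre-dose blood sample no stated role

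*Combined protocol and SAP*

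**What the plan says.** The biomarker paragraph of Section 8.4 has the markers "described with summary statistics (mean, median, standard deviation, range) at each time point" and, in the same sentence, "compared between the 5-AZA+ATRA and placebo using the Wilcoxon rank sum test statistics". It then states that a "linear mixed model with random effects will be applied to analyze the biomarker trajectories over time", and that "The biomarkers will be correlated with disease progression outcomes". It names no baseline, change score, covariate or period for the comparison, and no fixed effects for the model.

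Other sections bear on this:

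- **Design.** The Study Summary and Section 3.1 describe an open-label trial against no therapy. Section 3.1 adds: "During treatment phase 2, the 'no therapy' group will receive 5-AZA + ATRA on a 28-day cycle".
- **Blood sampling.** Section 7 (Treatment Phases): "Peripheral blood will also be collected at day 1 of study prior to Leuprolide administration and day 1 of each cycle". Table 8 lists marker blood every 4 weeks in the treatment phases and every 12 weeks in follow-up. Section 8.1 instead says "every 3 cycles, we will measure the dormancy biomarkers".
- **Marrow.** Section 7 and Table 8 make the aspirate optional and place it at the end of the study. Section 8.1 includes it in the 3-cycle schedule.
- **Marker and outcome.** The Study Summary relates markers to recurrence-free survival by "Kaplan-Meier curves stratified across biomarker abundance groups". Sections 3.3 and 3.3.1 define time to progression instead.

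**The concern.** Dormancy induction is the trial's hypothesis (Section 2), and relating markers to antitumour activity and progression is a secondary objective (Section 2.2). Whether the drug moves its own mechanism markers is therefore a result people will read.

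As written, an analyst cannot tell which samples form the two groups. The label matters because the no-therapy condition exists in the control arm only until Phase 2 dosing starts. The efficacy part of Section 8.4 handles this for progression, with period baselines, carryover and period terms, and PSADT stratification. None of it is carried over to the markers. With about 10 patients per arm, an ill-defined contrast could reverse or hide a real marker effect, and leaving out the pre-dose level could miss one.

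**Working it through.** **The plan's own figure.** No figure is stated for the marker analysis. It inherits the 20 patients of Section 8.2, justified there by a McNemar calculation for 20% vs 60% (two-sided 10%, 80% power; stated range 14-19). With d = 0.4 and discordance D:

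n = [1.645·√D + 0.842·√(D − d²)]² / d²

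- Full concordance, D = 0.40: n = 13.19, rounded up to 14.
- Independence, D = 0.2×0.4 + 0.6×0.8 = 0.56: n = 19.43, rounded up to 20.

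This agrees with the stated range apart from rounding. Randomisation is 1:1, so a between-arm marker test has about 10 patients per arm.

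**Who is on drug when.** Phase 1 starts on Day 29 and lasts three 28-day cycles: 29 + 3×28 = Day 113.

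| Interval | Drug-first arm | No-therapy arm |
|---|---|---|
| Day 1 to Day 29 | leuprolide only | leuprolide only |
| Day 29 to about Day 113 | on drug | no therapy |
| Phase 2, from about Day 113 | past its 3 cycles | on drug |
| Follow-up | exposed | exposed |

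**Reading A: groups are the randomised arms.** From Phase 2 the arm labelled as control is the one on drug. Illustration: 10 vs 10, normal data, 1 SD drug effect, two-sided 5% (assumed, as the plan gives no marker alpha), 4,000 simulated trials. The Phase 2 rank-sum is significant in favour of the original control arm in 51% of trials with no carryover and 16% with half carryover. With full carryover it is significant in about 4% in total, so a real effect is hidden.

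**Reading B: groups are treatment received, pooled over periods.** The same patients supply samples to both groups. The rank-sum test assumes independent samples, so its reference distribution no longer applies.

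**Phase 1 only.** The contrast is clean. With no effect, the unadjusted rank-sum rejects in 4.1-4.6% of trials, so the test is valid. The question is efficiency. With correlation ρ between pre-dose and later level, adjustment multiplies the residual variance by 1 − ρ², so a 1 SD shift becomes 1/√(1 − ρ²) residual SDs: 1.05 at ρ = 0.3, 1.15 at 0.5, 1.40 at 0.7 and 1.67 at 0.8. A plain change score has variance 2(1 − ρ), which exceeds 1 whenever ρ < 0.5. Simulated power, 10 vs 10, 1 SD shift, two-sided 5%:

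| Assumed ρ | Rank-sum, unadjusted | Rank-sum on change | Rank ANCOVA | Parametric ANCOVA |
|---|---|---|---|---|
| 0 | about 52% | 28% | 54% | 54% |
| 0.3 | about 52% | 39% | 55% | 58% |
| 0.5 | about 52% | 50% | 63% | 66% |
| 0.7 | about 52% | 74% | 76% | 82% |
| 0.8 | about 52% | 89% | 85% | 93% |

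ANCOVA costs nothing at low correlation and gains clearly from about 0.5. Change scores lose power below about 0.5, so adjusting for the baseline level is the safer choice.

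**Endpoint wording.** Patients enter with rising PSA after definitive local treatment, so they have already recurred. Recurrence-free survival is not among the endpoints in Sections 3.2, 3.3 or 8.1, and Section 8.4 itself relates markers to progression. The Study Summary phrase is the outlier.

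**The case against.** The strongest reply is that this is an under-specified secondary analysis in a 20-patient pilot, for which the Study Summary promises a descriptive summary of the marker panel. Several parts of that reply stand.

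- A reader might infer that the plan commits to testing raw levels at every visit. It does not say so. The time-point phrase attaches to the summary statistics, and the comparison clause gives neither time nor scale.
- A reader might infer that the pre-dose sample is ignored altogether. The mixed model of trajectories could use it and would respect repeated measures within patient. But its terms are not named, so it does not yet supply the missing contrast.
- The Phase 1 point concerns power, not validity, and the gain is only 2-3 percentage points at correlations of 0 to 0.3.
- A reader might infer that the marker-outcome curves will show spurious associations at a high rate. The documents do not support a large figure. They state no test, cut-point or grouping sample for those curves, and the trial's own crossover weakens the confounding by arm. Suppose the drug raises an inert marker and also delays progression. A pooled log-rank then rejects in about 17% of simulated trials if controls never cross over, but in 6-9% once they do, against a nominal 5%. Nor does any section group patients by their highest value over follow-up.

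What does not fall away is that the named comparator does not exist and that, without a period, both natural readings of the clause fail after Phase 1.

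**Conclusion.** The point holds as a defect of specification with a real consequence. The comparison needs a named comparator, a period and a role for the pre-dose sample. Phase 1 is the only period in which a between-arm test compares drug with no drug.

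The size is conditional. With a 1 SD effect, 10 patients per arm and two-sided 5%, baseline adjustment raises power from about 52% to 54-55% at correlations of 0 to 0.3 and to 63-85% at 0.5 to 0.8 (rank ANCOVA). The Phase 2 figures likewise rest on an assumed effect and carryover. The documents give no marker SD, effect or correlation, so these figures show direction and range only.

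The recurrence-free survival phrase needs a wording correction. It is not evidence of an additional endpoint. None of this touches the primary efficacy or safety analyses.

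**What to change.** 1. **Section 8.4, comparator.** Replace placebo with no therapy, both in the biomarker paragraph and where period-baseline variables are contrasted.
2. **Section 8.4, comparison.** Make the between-arm blood-marker comparison the end-of-Phase-1 level, by ANCOVA on the rank or log scale, with terms for arm, the Day 29 pre-dose level and PSADT stratum. State that both samples are drawn in both arms, the first before Phase 1 dosing and the second before Phase 2 dosing.
3. **Section 8.4, later samples and model.** Report samples from Phase 2 onward descriptively by sequence. If the mixed model is kept, name its treatment, period, time, baseline and PSADT terms.
4. **Study Summary.** Replace recurrence-free survival with time to disease progression. Base any marker-outcome analysis on the Day 29 pre-dose sample, with a stated cut-point, and stratify it by arm.
5. **Sections 7 and 8.1, Table 8.** Reconcile the marker frequency (every 4 weeks vs every 3 cycles) so that the Day 29 and end-of-Phase-1 samples are both assayed. Reconcile the marrow schedule too. With an optional aspirate at end of study only, marrow has no baseline and stays descriptive.

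The cost is mostly text. Section 7 and Table 8 already schedule the blood, so no added visits or patients are needed. The only possible extra is assay work, if the 3-cycle schedule was what the laboratory had planned.

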## **9. DATA HANDING AND RECORD KEEPING**

## **9.1 Electronic Data Capture (EDC) System**

All eCRFs will be entered directly into a web-based electronic research application portal known as eRAP. eRAP's role-based access control security and audit capability ensures that the research data is protected from unauthorized access, modification, and exposure. Key features of this web-based database system include allowing access and data entry from multiple sites, with each site having a separate pool of data as necessary. All data stored in the eRAP system is backed up daily. Detailed audit services include any data field level changes, who made the changes, when the changes were made, the old value and the new value. Data from eRAP can easily be extracted to excel or flat text file formats for easy import into SAS or other statistical software packages.

## **9.2 Verification of EDC System**

Once the database has been set up, the PI will test the system. The testing will include confirmation of the proper functioning of valid value checks, subject ID generation, derived variable computations, data extracts, and system reports.

## **9.3 Entering data**

Since electronic CRFs will be used, data entry will be conducted onsite by clinicians who have been granted appropriate access to do so.

## **9.4 Data Validation Process**

As part of the data validation process, edit check programs will be embedded in the database thru valid-value, valid-range and missing value alerts specified for each field as necessary. Valid-value edit checks include:

- Requiring the user to enter a coded value taken from a list that is presented on the CRF. If a value not on the list is entered the user will be prompted to check the value and enter a value on the list.
- Requiring the user to enter a value within a particular range of possible values for a continuous measure. If a value outside the range is entered the user will be prompted to check the value and re-enter.
  - In addition to the univariate field alerts specified above, there will be multivariate alerts built into the database design:
- Confirming that only valid options are selected in a 'choose all that apply' multiple choice field, where the range of options deemed valid depends on some other parameter.
- Confirming that diastolic blood pressure reading is less than the associated systolic blood pressure reading.
- Confirming that "other, specify" is completed when "other" is selected.
- Confirming that eligibility criteria are met.
- As well as cross-module alerts such as:
  - Comparing the dates and times of all assessment time points to confirm that they occur in an appropriate sequence.

## **9.5 Data Cleaning and Discrepancy Management**

Any discrepancies identified through this process will be highlighted and corrected in the system.

## **9.6 Data Security**

The EDC database is approved by Mount Sinai IT Security and HIPAA and operates using high-end servers located in the Secured Mount Sinai Data Center. All data stored in the eRAP system is backed up daily. Access to the database is controlled by policies requiring the PI to authorize user and user roles. Quick view audit service allows authorized user to see who accessed records for view or edit and detailed audit services include seeing any data field level changes, who made the changes, when the changes were made, as well as the value before and after the change.

## **9.7 Quality Control Procedures**

Comprehensive edit checks will be used to clean data. Patient data will be entered continuously. All changes to the data and the database structure will be recorded in an automatic audit trail. Random checks will be done by the PI to ensure data accuracy and completeness. A final database will be declared when all data has been entered, the data entry verified, the data validated and the database defined as clean. After declaration of a final database the data will be exported from eRAP to excel for import to SAS and both the database and the SAS datasets will be locked and protected from changes. All statistical analyses for the final analysis will be performed on the locked SAS datasets.

## **9.8 Medical and Adverse Event Coding**

Coding of Adverse Events occurring during the study will be performed by the Clinical Research Manager according to the revised CTCAE v4.0 while coding of concomitant medications, prior anti-cancer therapy and further therapy will be performed according to the World Health Organization-Drug Dictionary Enhanced (WHO-DDE). These dictionaries contain the respective classifications of adverse events and drugs in proper classes. When dictionary entries and verbatim terms (either for adverse events for medications) do not directly match, the PI will review the entry as well as other related information such as comment fields to identify the most appropriate match. In the event there are compound verbatim events (either AEs or medications) listed in the CRF, such events must be split into more than one record for purposes of medical coding. The PI will be responsible for splitting the compound events into separate entries.

## **9.9 Confidentiality**

Information about study subjects will be kept confidential and managed according to the requirements of the Health Insurance Portability and Accountability Act of 1996 (HIPAA). Those regulations require a signed subject authorization informing the subject of the following:

- What protected health information (PHI) will be collected from subjects in this study
- Who will have access to that information and why
- Who will use or disclose that information
- The rights of a research subject to revoke their authorization for use of their PHI.

In the event that a subject revokes authorization to collect or use PHI, the investigator, by regulation, retains the ability to use all information collected prior to the revocation of subject authorization. For

subjects that have revoked authorization to collect or use PHI, attempts should be made to obtain permission to collect at least vital status (i.e. that the subject is alive) at the end of their scheduled study period.

#### **9.10 Records Retention**

The Investigator must retain drug disposition records (if applicable), source documents, and case histories designed to record all observations and other data pertinent to the investigation (e.g. case report form) for the maximum period required by applicable regulations and guidelines, or Institution procedures.

If a change in the PI occurs, the records shall be transferred to a mutually agreed upon designee (e.g., another Investigator, IRB).

#### **9.11 Subject Privacy**

Patients will be informed of the extent to which their confidential health information generated from this study may be used for research purposes. Following this discussion, they will be asked to sign the HIPAA form and informed consent documents. The original signed document will become part of the patient's medical records, and each patient will receive a copy of the signed document. The use and disclosure of protected health information will be limited to the individuals described in the informed consent document.

It is the responsibility of the research staff to ensure that protocol subjects received, understands, and signs the informed consent document before enrolling the patient onto this trial. Personnel must provide a HIPAA form and obtain acknowledgment before the subject participates in this study.

All subject data will be identified by a subject identification number and subject initials only, to protect the subject's privacy. The data will be blinded accordingly in all data analysis. However, in compliance with federal guidelines, the investigator will permit a representative from Mount Sinai Health System audit committee to review that portion of the subject's medical record that is directly related to the study. This will include all relevant study documentation including medical histories to verify eligibility, laboratory test results to verify transcription accuracy, X-ray reports, admission/discharge summaries for hospital/outpatient admissions while the subject is on-study and autopsy reports for deaths occurring during the study. As part of the required content of informed consent, the subject will be informed that his medical record may be reviewed. Should access to the medical record require a separate waiver or authorization, it is the PI's responsibility to obtain such permission from the patient in writing before the subject is entered into the study.

